5.3. Clinical Trial Rationale

The parent trials provided opportunities for adult patients with RMS to participate in important Phase 3 clinical trials to determine if RPC1063 is effective and safe, and to participate in a clinical pharmacology study characterizing the multiple-dose PK and PD of RPC1063 in patients with RMS. This open-label extension (OLE) trial is designed to further characterize the longer-term safety and efficacy beyond that required for the Phase 3 registration trials. In addition, the trial allows all patients who are receiving clinical benefit from treatment with RPC1063 to continue to receive it until the end of the trial or until the Sponsor discontinues the development program.

6. TRIAL OBJECTIVES AND ENDPOINTS

6.1. Primary Objective

To characterize the long-term safety and tolerability of RPC1063 in patients with relapsing multiple sclerosis.

6.2. Secondary Objectives

To characterize the long-term efficacy of RPC1063 in patients with relapsing multiple sclerosis.

6.3. Endpoints

6.3.1. Safety Endpoints

Safety and tolerability will be characterized in this trial by the incidence, relationship, and type of adverse events, serious adverse events, and adverse events leading to withdrawal from the trial; the incidence, relationship, and type of laboratory abnormalities; vital signs; electrocardiogram (ECG) results; and physical examination abnormalities. Suicidality (Columbia-Suicide Severity Rating Scale [C-SSRS]) will be assessed in the trial. In addition, descriptive characterization will be provided for adverse events of special interest (AESIs) including bradycardia and heart conduction abnormalities (ECG and vital signs), pulmonary effects (forced expiratory volume at 1 second [FEV₁], forced vital capacity [FVC], and diffusing capacity of the lung for carbon monoxide measurements), macular edema (optical coherence tomography [OCT]), hepatic effects (liver function tests), serious or opportunistic infections, and malignancy (see Section 12.4.2 for the complete list of AESIs).

Exploratory measurements of immune response (eg, anti-SARS-CoV-2 serology) will be assessed from blood samples collected at trial visits and end of treatment, and the potential association between these measurements and selected endpoints related to safety and/or efficacy.

In addition, dependence and withdrawal symptoms will be assessed in at least 80 evaluable patients who discontinue study drug using the following assessments: physician's withdrawal checklist (PWC-20), hospital anxiety and depression scale (HADS), Epworth sleepiness scale (ESS), vital signs, and the C-SSRS. Changes from last on study-drug assessment for each withdrawal scale (PWC-20, HADS, ESS, C-SSRS, and vital signs) to post study drug Days 1, 4, 7, 14, 21, and 90 will be summarized.

6.3.2. Efficacy Endpoints

- Annualized relapse rate
- Time to first relapse
- The number of new or enlarging hyperintense T2-weighted brain magnetic resonance imaging (MRI) lesions at each visit
- The number of gadolinium-enhanced brain MRI lesions at each visit

- Time to onset of disability progression as defined by a sustained worsening in Expanded Disability Status Scale (EDSS) of 1.0 points or more from baseline, confirmed after 3 months and after 6 months
- Proportion of patients who are free of gadolinium-enhanced lesions at each visit
- Proportion of patients who are free of new or enlarging T2 lesions at each visit
- Percent change in normalized brain volume (atrophy) on brain MRI scans from Baseline at each visit
- Change in Multiple Sclerosis Functional Composite (MSFC) score from Baseline at each applicable visit (including the Low-Contrast Letter Acuity Test [LCLA] measurement of visual function as a component)
- Change in Multiple Sclerosis Quality of Life 54 score from Baseline at each applicable visit
- Changes in other MRI variables including number and volume of gadolinium-enhanced T1 lesions, volume of T2 lesions, number of new or enlarging T2 lesions, volume of unenhancing T1 lesions, number of new unenhancing T1 lesions

7. INVESTIGATIONAL PLAN

7.1. Overall Trial Design

This is a multi-site, open-label extension trial of oral RPC1063 (ozanimod HCl) 1 mg (equivalent to ozanimod 0.92 mg) administered once daily to patients with RMS who are eligible according to the enrollment criteria and completed one of the following trials: RPC01-201, RPC01-301, or RPC01-1001 (the “parent trials”).

Based on an estimated dropout rate of 10% per year, approximately 2350 patients may be eligible for enrollment in the trial depending on completion of one of the parent trials.

Regardless of treatment assignment in the parent trial, patients will receive RPC1063 at a dose of 1 mg daily in RPC01-3001 after a 7-day dose escalation regimen, as applicable (Section 9.1). Approval from the Sponsor’s representative is required for enrollment more than 14 days after the patient’s last dose of investigational drug in the parent trial, and the patient must undergo RPC1063 dose escalation. Patients from either the blinded extension of the RPC01-201 Part A trial or the RPC01-1001 trial will not require initial dose escalation unless the duration between the last dose of RPC1063 in the parent trial and the first dose in RPC01-3001 is more than 14 days. Patients will receive RPC1063 at 1 mg/day until the end of the trial or until the Sponsor discontinues the development program.

It is anticipated that the trial will include approximately 275 sites in North America, Europe, South Africa, and New Zealand that participated in one or more of the parent trials.

Scheduled trial visits include:

- Baseline (Day 1)
- Evaluations every 3 months (91 days) and every 12 months, as specified in the schedule of events (Table 2). After a patient reaches their 3rd annual visit, the Every 3-Month Visit will become the Every 6 Month Visit (one visit between annual visits instead of 3). Annual visits (Every 12 Months) are unchanged.
- Early Termination/End of Treatment visit
- Visits at 1, 4, 7, 14, and 21 days after the last dose of investigational drug to assess dependence and withdrawal symptoms
- Absolute lymphocyte count (ALC) Follow-up Visit(s) every 14 days (\pm 3 days) after the last dose of investigational drug until ALC is above the lower limit of normal (LLN) (the Medical Monitor should be consulted if the ALC is not $>$ LLN by the Day 90 Safety Follow-up Visit, and ALC visits should continue every 14 days (\pm 3 days) until the Investigator is notified to discontinue).
- Safety Follow-up Visit 28 days after the last dose of investigational drug
- Safety Follow-up Visit 90 days after the last dose of investigational drug

- In the event that commercial ozanimod or an access program becomes available prior to December 2022, subjects may transition to the commercial product after discussion with the Investigator at his/her discretion. Subjects who transition to commercial ozanimod are not required to attend safety follow-up visits after their end of treatment visit as long as commercial ozanimod is started within 14 days of discontinuation of study drug. Otherwise, all other subjects continuing in the study and subsequently discontinuing prior to the availability of commercial ozanimod in their country/state or by end of the study will be required to follow the schedule of assessments through the safety follow up visits.

Trial assessments are described in [Table 2](#). These include evaluation of adverse events (AEs), review of concomitant medications, clinical laboratory tests, assessment of immune response, PK sampling, physical and neurological examination (MRI with and without gadolinium contrast), vital sign measurements, 12-lead ECG, OCT, pulmonary function tests, dermatological examination, and C-SSRS evaluation. The Cognitive Function subscale of the Multiple Sclerosis Quality of Life-54 (MSQOL-54) will be assessed to evaluate quality of life and subjective cognitive impairment. In addition to the C-SSRS, the PWC-20, the HADS, and the ESS will be administered to assess dependence and withdrawal symptoms. These assessments will be administered on at least 1 visit while on study drug and in at least 80 evaluable patients after discontinuing study drug ([Table 3](#)). All patients should undergo these assessments until the Sponsor decides that no further withdrawal assessments are required.

Refer to [Table 2](#) for instructions regarding baseline assessments.

For patients from RPC01-1001, the RPC01-3001 informed consent process may begin on the last day of dosing in RPC01-1001. For the same patients, Baseline (Day 1) brain MRI, OCT, and pulmonary function tests are not required to occur on the same day; these may be performed at any time between signing informed consent and first dose of RPC1063 in RPC01-3001. The RPC01-1001 End of Study assessments and the RPC01-3001 Baseline procedures may be performed on the same day. The first dose of RPC1063 in RPC01-3001 may only be administered after completion of all RPC01-1001 End of Study assessments and all RPC01-3001 Baseline assessments.

If a patient experiences a relapse after completing a parent trial, but prior to entering RPC01-3001, the patient may remain eligible for RPC01-3001. There is no minimum waiting period following the relapse; however, the Investigator should confirm that the patient is neurologically and medically stable prior to initiating investigational drug. If the Investigator suspects the patient may require more than 14 days after the last dose of investigational drug in the parent trial to become stable, the Investigator should discuss this immediately with the Sponsor's representative to determine ongoing eligibility.

Patients will be evaluated for relapses throughout the trial, including during the Safety Follow-up Visit, and patients will be instructed to contact the treating Investigator for any new or worsening neurological symptoms during the trial that may indicate a possible relapse. If the Investigator suspects a possible relapse, an unscheduled visit is to be planned as soon as possible, ideally within 7 days of symptom onset. A relapse is defined as the occurrence of new or worsening

neurological symptoms attributable to MS and immediately preceded by a relatively stable or improving neurological state of at least 30 days.

The new or worsening neurological symptoms must be accompanied by objective neurological worsening, based on examination by the evaluator, consistent with an increase of at least half a point on the EDSS, or 2 points on one of the appropriate Functional System (FS) scores, or 1 point on two or more of the appropriate FS scores compared to last rating (EDSS or FS scores) that did not occur during a relapse. The change in FS scale scores should correspond to the patient's symptoms (eg, patient reported change in visual acuity should correspond to a change in the vision FS score). Symptoms must persist for > 24 hours and should not be attributable to confounding clinical factors (eg, fever, infection, injury, adverse reactions to concomitant medications).

A blood sample will be collected at the subject's next visit after this amendment is implemented, every 6 months thereafter, and at the end of treatment for measurements of immune response (eg, SARS-CoV-2 serology).

Patients who are withdrawn early from the trial will be required to return to the trial site as soon as possible so that the final assessments can be conducted. Patients who withdraw from the trial will be followed for collection of safety data, including lymphocyte recovery. In addition, PK samples will be collected at the End of Treatment/Early Termination Visit and for Day 28 and Day 90 Safety Follow-up Visits.

7.2. Dose Adjustment Criteria

There is no provision for dose adjustments in this trial. Patients who cannot tolerate investigational drug must be withdrawn from the trial.

Procedure	Baseline (Day 1)^a	Every 3/6 Months^p (± 10 days)	Every 12 Months (± 10 days)	Unscheduled Relapse Visit^b	End of Treatment/ Early Term^c	ALC Follow- up Visit^c (every 14 days after last dose ± 3 days)	Safety Follow- up Visit^q (28 days after last dose ± 7 days)	Safety Follow- up Visit^{m, q} (90 days after last dose ± 10 days)
Brain MRI ⁿ	X ⁱ		X		X			
EDSS and neurological examination	X ^a	X	X	X	X			
MSFC and LCLA	X ^a		X	X	X			
MSQOL-54	X ^a		X		X			
Pulmonary function tests ^j	X ^a		X		X			
OCT ^k	X ^a		X		X			
Dermatological (skin) examination	X ^a		X		X			
Columbia-Suicide Severity Rating Scale (C-SSRS)	X ^a	X	X	X	X		X	X
Prior/concomitant therapy	X	X	X	X	X		X	X
AEs/SAEs	X	X	X	X	X		X	X
PK Sampling					X ^o		X ^o	X ^o
Blood Sample ^r	A blood sample will be collected at the patient's next visit after this amendment is implemented, every 6 months thereafter, and at the end of treatment for potential measurements of immune response (eg, SARS-CoV-2 serology).							

Confidential and Proprietary

Footnotes are provided on the next page.

- ^a Perform specified procedures at Baseline (Day 1) only if they were not performed at the end of treatment/study visit of the parent trial or not within the timeframe prior to the end of treatment/study visit specified by the parent trial protocol. Perform a urine pregnancy test at Baseline if more than 1 month has elapsed from the last pregnancy test in the parent trial. Approval from the Sponsor's representative is required for enrollment more than 14 days after the patient's last dose of investigational drug in the parent trial, and the patient must undergo RPC1063 dose escalation. For patients from RPC01-1001, the RPC01-3001 informed consent process may begin on the last day of dosing in RPC01-1001. For the same patients, Baseline (Day 1) brain MRI, OCT, and pulmonary function tests are not required to occur on the same day; these may be performed at any time between signing informed consent and first dose of RPC1063 in RPC01-3001. The RPC01-1001 End of Study assessments and the RPC01-3001 Baseline procedures may be performed on the same day.
- ^b The Unscheduled Relapse Visit will be conducted if a possible relapse is suspected at any time prior to the 90-Day Safety Follow-up Visit. The visit is to be planned as soon as possible, ideally within 7 days of symptom onset. If the relapse is confirmed, the Unscheduled Relapse Visit and Early Term procedures may occur at the same visit. If the relapse is not confirmed, patients should return to their usual visit schedule.
- ^c Central laboratory testing of ALC will continue every 14 days (\pm 3 days) after discontinuation of RPC1063 or the End of Treatment/Early Termination Visit until ALC is above the lower limit of normal for patients who discontinue treatment. If an ALC Follow-up Visit is needed within the window of the 90-Day Safety Follow-up Visit, the patient should only return for the 90-Day Safety Follow-up Visit and ALC should be collected at that visit. If a patient has started a lymphocyte-depleting treatment during the safety follow up period, ALC should only be determined at the 90-Day Safety Follow-up Visit. The Medical Monitor should be consulted if the ALC is not $>$ LLN by the Day 90 Safety Follow-up Visit for subjects without lymphocyte depleting DMTs and ALC visits should continue every 14 days (\pm 3 days) until the Investigator is notified to discontinue.
- ^d Baseline (Day 1), 28-Day Safety Follow-up Visit, End of Treatment/Early Termination clinical laboratory tests include chemistry (full panel), hematology, and urinalysis. Every 3/6 months clinical laboratory tests include: Chemistry (abbreviated panel) and hematology. Every 12 months (annually) clinical laboratory tests include: Chemistry (full panel) and hematology.
- ^e Urine beta-human chorionic gonadotropin (hCG) test at each visit for women of childbearing potential only. Between scheduled visits up until the 90-Day Safety Follow-up Visit, monthly home urine pregnancy tests should be performed by the patient. If a urine pregnancy test result is positive, the Investigator will instruct the patient to suspend further RPC1063 dosing, if applicable, and schedule a follow-up appointment as soon as possible. A serum pregnancy test will be performed for confirmation, including after the 90-Day Safety Follow-up Visit, if needed.
- ^f Vital signs will be collected at pre-dose and every hour (\pm 10 min) for 6 hours post-dose unless the patient is entering the trial from Trial RPC01-201 Part A or Trial RPC01-1001 and does not require dose escalation. For these patients, the End of Treatment vital signs from Trial RPC01-201 Part A or End of Study vital signs from Trial RPC01-1001 will be used as the baseline vital signs for the current trial.
- ^g ECG will be performed at pre-dose and 6 hours post-dose unless the patient is entering the trial from Trial RPC01-201 Part A or Trial RPC01-1001 and does not require dose escalation. Baseline or pre-dose ECG should be provided by the site and be available for comparison to the post-dose ECG in order to determine if discharge criteria are met.
- ^h The investigational drug regimen will begin with a 7-day dose escalation regimen: RPC1063 0.25 mg on Days 1 to 4, 0.5 mg on Days 5 to 7, and 1 mg from Day 8 onward. Patients from either the blinded extension of the RPC01-201 Part A trial or the RPC01-1001 trial will not require initial dose escalation unless the duration between the last dose of RPC1063 in the parent trial and the first dose in RPC01-3001 is more than 14 days.
- ⁱ The brain MRI must be performed at Baseline (Day 1) if the last MRI in the parent trial was performed \geq 6 months prior to entry into the current trial. For patients who enter RPC01-3001 from parent trial RPC01-1001, the Baseline (Day 1) brain MRI may occur at any time between signing of informed consent and the first dose of RPC1063 in RPC01-3001.

- ^j Pulmonary function tests will include forced expiratory volume at 1 second (FEV₁) and forced vital capacity (FVC) measurements at all the above indicated visits. In addition, diffusing capacity of the lung for carbon monoxide (DLCO) will be assessed where locally available. DLCO will only be assessed at the End of Treatment/Early Termination Visit. If any abnormalities occur, they will be followed until such time as resolution is confirmed or no further improvement is expected by the Investigator (based on a follow-up period of not less than 3 months).
- ^k If abnormal OCT findings, or visual signs or symptoms of macular edema are observed, a general ophthalmologic examination including eye history, visual acuity, and dilated ophthalmoscopy will also be performed.
- ^l Patients from Trial RPC01-201 Part A who do not require dose escalation or cardiac safety monitoring may have the parent trial End of Treatment visit on the same day as the Baseline visit for this trial. If the patient has already taken RPC1063 that day, a duplicate dose should not be taken. The first dose for the current trial may be dispensed at the Baseline visit to allow administration the following day.
- ^m The 90-Day Safety Follow-up Visit should be conducted as a clinic visit. However, if the patient is not available for a clinic visit, a telephone call follow-up should be performed (with at least 3 attempts within the visit window) to record the pregnancy test result, concomitant medications, and AEs, including information regarding relationship of AEs to RPC1063.
- ⁿ MRI scans should not be performed until 30 days after the last dose of methylprednisolone treatment for relapse. Previously scheduled MRIs should be rescheduled as necessary if a relapse occurs (see Section 11.1).
- ^o Samples will be collected at the End of Treatment/Early Termination Visit and for Day 28 and Day 90 Safety Follow-up Visits.
- ^p After a patient reaches their 3rd annual visit, the Every 3 Month Visit will become the Every 6 Month Visit (one visit between annual visits instead of 3). Annual visits (Every 12 months) are unchanged.
- ^q In the event that commercial ozanimod or an access program becomes available prior to December 2022, subjects may transition to the commercial product after discussion with the Investigator at his/her discretion. Subjects who transition to commercial ozanimod are not required to attend safety follow-up visits after their end of treatment visit as long as commercial ozanimod is started within 14 days of discontinuation of study drug. Otherwise, all other subjects continuing in the study and subsequently discontinuing prior to the availability of commercial ozanimod in their country/state or by end of the study will be required to follow the schedule of assessments through the safety follow up visits.
- ^r Assessment of immune response may also include analyzing stored blood collected during previous visits prior to implementation of amendment 10.

Abbreviations: AEs/SAEs = adverse events/serious AEs; ALC = absolute lymphocyte count; DMTs = disease modifying therapies; EDSS = Expanded Disability Status Scale; ECG = electrocardiogram; MRI = magnetic resonance imaging; LCLA = Low-Contrast Letter Acuity Test; LLN = lower-limit of normal; MSFC = Multiple Sclerosis Functional Composite; MSQOL-54 = Multiple sclerosis quality of life; OCT = optical coherence tomography.

Table 3: Dependence and Withdrawal-related Assessments

Visit Assessment	On Study-Drug Visit ^a	End of Treatment/Early Termination ^b	Follow-up Visit Day 1 (+1d) ^c	Follow-up Visit Day 4 (±1d) ^c	Follow-up Visit Day 7 (±2d) ^c	Follow-up Visit Day 14 (±3d) ^c	Follow-up Visit Day 21 (±3d) ^c	Follow-up Safety Visit Day 90 (±10d) ^c
Vital signs ^d	X	X	X	X	X	X	X	X
PWC-20	X	X	X	X	X	X	X	X
HADS	X	X	X	X	X	X	X	X
ESS	X	X	X	X	X	X	X	X
C-SSRS ^d	X	X	X	X	X	X	X	X
Concomitant medications ^d	X	X	X	X	X	X	X	X
AEs/SAEs ^d	X	X	X	X	X	X	X	X

^a The “On Study-Drug Visit” assessments should be performed at the first scheduled visit after Protocol Amendment 8 is approved at the site and the patient has been re-consented. It serves to provide a baseline assessment on study drug, particularly for patients who discontinue study drug before the End of Treatment/Early Termination Visit.

^b Patients should schedule the End of Treatment/Early Termination Visit within 24 hours of study drug discontinuation, as appropriate.

^c If an on-site study visit cannot be performed, the PWC-20, C-SSRS, HADS, and ESS should be assessed remotely. Patients should be encouraged to complete all follow-up visits according to the visit schedule. If a patient does not return to the site for a visit, at a minimum, the site must attempt to contact the patient (eg, by phone) for a remote assessment of the PWC-20, C-SSRS, HADS, ESS, concomitant medications, and AE/SAEs.

^d If these assessments are performed as part of a scheduled visit procedure in [Table 2](#), then they do not have to be repeated on the same day for dependence withdrawal assessments.

Abbreviations: AEs = adverse events; C-SSRS = Columbia-Suicide Severity Rating Scale; d = day; ESS = Epworth sleepiness scale; HADS = hospital anxiety and depression scale; PWC-20 = Physician’s withdrawal checklist; SAEs = serious adverse events.

Table 4: Cardiac Monitoring During Dose Escalation

Procedure ^a	Day 1		
	Pre-dose	Hours 1, 2, 3, 4, 5 (± 10 min)	Hour 6 (± 10 min)
Vital signs ^b	X	X	X
12-lead ECG	X ^c		X
Assess Discharge Criteria ^d			X

^a These assessments should also be conducted at the indicated times on Days 5 and 8 if issues are identified on the prior dose escalation day. These Day 1 assessments are not required if the patient is entering the trial from Trial RPC01-201 Part A or Trial RPC01-1001 and does not require dose escalation.

^b Resting heart rate and blood pressure in the sitting position at each time point.

^c Baseline or pre-dose ECG should be available for comparison to the post-dose ECG in order to determine if discharge criteria are met.

^d See Section 12.1.11 for monitoring patients for discharge status. Additional observation should be instituted until resolution of the following: heart rate (per hourly vital signs measurement) 6 hours post-dose is < 45 bpm and > 10 bpm below pre-dose; heart rate (per hourly vital signs measurement) 6 hours post-dose is at the lowest value post-dose; ECG 6 hours post-dose shows new onset second degree or higher atrioventricular (AV) block; the ECG 6 hours post-dose shows a prolonged QTcF interval (> 450 msec men, > 470 msec women).

Abbreviations: ECG = electrocardiogram; QTcF = Fridericia's corrected QT interval.

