All patients who withdraw from the trial should complete an Early Termination Visit. Patients should be instructed to contact the Investigator (e.g. by phone) if they plan to withdraw from the study to discuss study drug discontinuation plans, and schedule the dependence and withdrawal assessment visits. Central laboratory testing of ALC will continue every 14 days (\pm 3 days) after discontinuation of RPC1063 or the End of Treatment/Early Termination Visit until ALC is above the lower limit of normal or until the Investigator is notified to discontinue (Section 12.2.1). Patients should be encouraged to complete the ALC and Safety Follow-up Visits for the

collection of safety data, including lymphocyte recovery, PK sampling, and to assess their disease status. Treatment for MS can be started after the 28-Day Safety Follow-up Visit based on Section 9.5.

The reason for withdrawal from the trial will be recorded in the clinical records and the patient's electronic case report form (eCRF). For those patients whose status is unclear because they fail to appear for trial visits without stating an intention to withdraw from trial participation, the Investigator should document in the source documents the steps taken to contact the patient (eg, dates of telephone calls, registered letters) prior to withdrawing the patient from the trial.

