11.3. Relapse Assessment

A relapse is defined as the occurrence of new or worsening neurological symptoms attributable to MS and immediately preceded by a relatively stable or improving neurological state of at least 30 days. The new or worsening neurological symptoms must be accompanied by objective neurological worsening consistent with an increase of at least half a point on the EDSS, or 2 points on one of the appropriate FS scores, or 1 point on two or more of the appropriate FS scores compared to last rating (EDSS or FS scores) that did not occur during a relapse. The change must be documented by the evaluator at either scheduled or unscheduled visits and must affect the FS scales that correspond to the patient's symptoms (eg, pyramidal, cerebellar, brainstem, sensory, bowel or bladder, visual, or cerebral). Symptoms must persist for > 24 hours

and should not be attributable to confounding clinical factors (eg, fever, infection, injury, adverse reactions to concomitant medications). When a patient experiences new or worsening symptoms at any time prior to the 90-Day Safety Follow-up Visit that may indicate a possible relapse, he/she should telephone the treating Investigator within 48 hours of symptoms onset. The treating Investigator (or designee) will conduct a telephone questionnaire and, as necessary, will arrange an Unscheduled Relapse Visit. The visit is to be planned as soon as possible, ideally within 7 days of symptom onset.

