11.4. Multiple Sclerosis Disability Progression

MS disability progression is defined as a sustained worsening in EDSS of 1.0 points or more from baseline, confirmed after a 3-month and 6-month period. Confirmation of MS disability progression must not occur at the time of a relapse. If the patient is scheduled to be evaluated to confirm their disability at the time of a relapse, the disability event must be assessed at a later visit, which may be the next scheduled visit, or an unscheduled visit conducted after the relapse has resolved. In case of MS disability progression the treating Investigator will discuss with the patient the treatment alternatives outside of the study.

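### Table 2 has no EDSS after Early Term, so a worsening still unconfirmed when a patient leaves counts as progression only if the site chooses to re-examine

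*Combined protocol and SAP*

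**What the plan says.** Table 2 (Section 7.3) has a row for "EDSS and neurological examination". It is marked at Baseline, Every 3/6 Months, Every 12 Months, the Unscheduled Relapse Visit and End of Treatment/Early Term. It is blank at the ALC, 28-Day and 90-Day follow-up visits. The C-SSRS row of the same table is marked at Day 28 and Day 90, so the blanks are not a fault in reading the table.

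Footnote b to Table 2 reads: "If the relapse is confirmed, the Unscheduled Relapse Visit and Early Term procedures may occur at the same visit".

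Section 11.4 defines progression as an EDSS worsening of at least 1.0 from baseline, confirmed at 3 and at 6 months. It then says: "Confirmation of MS disability progression must not occur at the time of a relapse". An assessment that falls in a relapse "must be assessed at a later visit, which may be the next scheduled visit, or an unscheduled visit conducted after the relapse has resolved". It adds: "In case of MS disability progression the treating Investigator will discuss with the patient the treatment alternatives outside of the study".

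Section 8.2 lists lack of efficacy as a reason for withdrawal. It encourages leavers to attend the follow-up visits for "collection of safety data, including lymphocyte recovery, PK sampling, and to assess their disease status".

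Section 12.1.1 treats the EDSS as the neurological examination and allows that examination at an unscheduled visit if warranted.

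Section 13.3.3 analyses time to 3-month and to 6-month confirmed progression separately by Kaplan-Meier, reporting the median and its 95% CI.

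**The concern.** Take a patient whose EDSS at exit is 1.0 or more above baseline and not yet confirmed. The exit EDSS may have been taken in a relapse, which footnote b allows. Section 11.4 then calls for a later assessment, but none of this patient's remaining scheduled visits carries an EDSS, although 8.2 gives those visits a disease-status purpose. Unless the site arranges an unscheduled EDSS, the worsening stays unconfirmed and the patient is presumably censored at exit.

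Kaplan-Meier assumes that censored patients have the same later risk as those who stay. Here worsening can be the reason for leaving: lack of efficacy is a listed withdrawal reason, and 11.4 has the investigator discuss treatment outside the study once progression occurs. Censoring is then related to the outcome. The error runs one way and makes confirmed progression look rarer than it is. What is at stake is how well one listed efficacy endpoint describes long-term disability. The primary safety objective is not touched.

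**Working it through.** The plan states no figure for this point, so there is none to reproduce.

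**1. Schedule against definition.** After Early Term the scheduled visits are ALC, Day 28 and Day 90, none with an EDSS. Section 11.4 needs a later EDSS outside a relapse. The only routes left are a visit for a newly suspected relapse, which cannot confirm if that relapse is real, and an unscheduled EDSS at the site's choice.

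**2. Could Day 90 serve for confirmation?** Early Term should fall within 24 hours of the last dose (Table 3, footnote b). The Day 90 visit has a window of 10 days either side, so it falls on days 80 to 100. The gap from Early Term is 80 − 1 = 79 to 100 − 0 = 100 days. On-trial 3-monthly visits are 91 days apart, each within 10 days, so the gap between them can be 91 − 20 = 71 to 91 + 20 = 111 days. Day 90 lies inside the spacing that already serves for 3-month confirmation. It cannot serve for 6 months (2 × 91 = 182 days).

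**3. Ordinary exit before confirmation.** With annual dropout d, the chance of leaving within t days is 1 − (1 − d)^(t/365.25). At the protocol's d = 10% this is 1 − 0.9^(91/365.25) = 2.6% for 3 months and 1 − 0.9^(182/365.25) = 5.1% for 6 months. If dropout after a worsening were 20% to 50% per year (an assumption), it would be 5.4% to 15.9% and 10.5% to 29.2%.

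**4. Illustration of the effect on the curve.** The documents do not give p, the share of relapses at which the patient leaves, so p is varied. The simulation used 30,000 to 40,000 patients per setting, with identical rates for all. Its other assumptions are:
- relapse rate 0.2 per year, with probability 0.2 that a relapse leaves a sustained step of 1.0 or more;
- background sustained worsening 0.01 per year;
- total exit hazard −ln(0.9) = 0.105 per year, of which 0.2p occurs at relapses;
- 5 years of potential follow-up;
- confirmation by an EDSS at least 71 days later (3-month) or 162 days later (6-month), outside a relapse;
- no unscheduled EDSS after exit, and unconfirmed worsening censored at exit.

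Kaplan-Meier estimates at 3 years (%), with the shortfall in percentage points in brackets:

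| p | All sustained worsenings | 3-month confirmed | 3-month with Day 90 EDSS, 80% attending | 6-month confirmed |
|---|---|---|---|---|
| 0 | 13.9 | 13.6 (0.3) | 13.9 (under 0.1) | 13.3 (0.6) |
| 5% | 13.8 | 13.0 (0.8) | 13.7 (0.1) | 12.7 (1.1) |
| 10% | 13.7 | 12.3 (1.4) | 13.4 (0.3) | 12.0 (1.7) |
| 25% | 13.7 | 10.8 (2.9) | 13.2 (0.5) | 10.5 (3.2) |

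An independent rerun agreed on the relative shortfalls to within about 0.7 points. The p = 25% row is extreme: exits at relapse would be 0.2 × 0.25 = 0.05 of a 0.105 hazard, about 47% of all exits. At p = 10% the share is 0.02/0.105 = 19%.

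**5. The median.** A constant hazard giving 13.9% at 3 years is −ln(0.861)/3 = 0.050 per year. Over the estimated trial span of 7.08 years (November 2015 to December 2022), 1 − exp(−0.050 × 7.08) ≈ 30% would progress. The median would fall near ln(2)/0.050 ≈ 14 years, so it is not reached with or without the gap.

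**The case against.** The strongest reply is that the protocol already provides the measurement. Section 11.4 allows an unscheduled visit after the relapse resolves, and 12.1.1 allows an EDSS at an unscheduled visit if warranted, so no extra Table 2 column is needed. This stands in part. A reader might infer that a worsening pending at exit can never become an event. For 3-month confirmation the documents do not support that: the visit is permitted, only not required. For a worsening first seen at exit, 6-month confirmation would need an EDSS beyond the last scheduled safety visit.

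A reader might also infer that Table 2 contradicts 7.1, which says: "Patients will be evaluated for relapses throughout the trial, including during the Safety Follow-up Visit". It does not. The Unscheduled Relapse Visit, which carries an EDSS, remains available until the 90-Day visit.

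Nor should one infer that everyone who leaves at a relapse has a pending progression. A relapse can rest on "objective neurological worsening consistent with an increase of at least half a point on the EDSS" or on functional-system changes, whereas progression needs 1.0. Footnote b is not a stopping rule either: 9.4 provides for treating relapses on study, and patients who stay keep the usual EDSS schedule.

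The sizes rest on assumed rates with unscheduled confirmation set to zero, so they overstate the effect wherever sites do re-examine. This objection stands.

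The Day 90 repair depends on accepting visit windows. If a strict 91-day minimum were required, a rerun left relative shortfalls of about 6% at p = 10% and 13% at p = 25% (0.06 × 13.7 = 0.8 and 0.13 × 13.7 = 1.8 points), against 0.3 and 0.5 in the table.

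Finally, the handling of unconfirmed worsening may be in a separate SAP, which 11.5 mentions. Its absence from 13.3.3 is therefore not counted as a fault. A SAP rule cannot, however, supply a measurement that was not taken.

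Ending EDSS at end of treatment can be defended when the aim is on-drug efficacy. It still leaves the pending cases unresolved.

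**Conclusion.** The gap is real and minor. After Early Term, confirming a pending worsening depends on a site's discretion, and because worsening can prompt exit, the 3-month and 6-month curves are biased downward. The size cannot be computed from the documents. The illustrative range is about 0.3 to 1.4 percentage points at 3 years for 3-month confirmation, with 0 to 10% of relapses leading to exit, the rates listed above, censoring at exit and no unscheduled EDSS. For 6-month confirmation the same runs give 0.6 to 1.7 points.

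A reader might infer that the reported median is wrong. It is unlikely to be affected, because on these rates it is not reached; what moves is the curve. The trial is single-arm with no hypothesis testing, so no comparison or test within it is distorted.

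**What to change.** In Table 2, add an EDSS at the 90-Day Safety Follow-up Visit only for patients whose End of Treatment/Early Term EDSS is 1.0 or more above baseline and unconfirmed. Do not count it if the patient is in relapse that day. State that it is accepted as 3-month confirmation within the protocol visit windows. Flag scores taken after another MS treatment was started following Day 28, as 9.5.2 allows.

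In 13.3.3, report how many worsenings were unconfirmed at the last EDSS, and add one supportive Kaplan-Meier run for each confirmation period that counts them as events, as an upper bound. For 6-month confirmation that run is the only remedy. It uses data already collected, so it remains possible even if the visit change comes too late.

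The cost is one short examination at an existing clinic visit and two or three sentences of analysis text. In the simulation 23 to 57 of 2350 patients had a sustained worsening with no later EDSS for 3-month confirmation when p was 0 to 10%. The number examined would be larger, because some worsenings at exit will not last. Some of these scores will reflect time off drug. Patients reached only by telephone (footnote m) and those who move to commercial ozanimod without follow-up visits (footnote q) would remain unconfirmed and stay in the reported count.
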